#### 8.2 Statistical Analysis Plan (SAP)

This section outlines the statistical analysis strategy and procedures for the study. If, after the study has begun, changes are made to primary and/or key secondary hypotheses, or the statistical methods related to those hypotheses, then the protocol will be amended (consistent with ICH Guideline E-9). Changes to exploratory or other non-confirmatory analyses made after the protocol has been finalized, along with an explanation as to when and why they occurred, will be listed in the Clinical Study Report (CSR) for the study. Post hoc exploratory analyses will be clearly identified in the CSR. See the statistical analysis plan (SAP) for more information.

#### 8.3 Hypotheses/Estimation

Objectives and hypotheses of the study are stated in Section 3.

#### 8.4 Analysis Endpoints

#### 8.4.1 **Efficacy Endpoints**

Radiographic Complete response (rCR) rate: proportion of subjects in the analysis population who have a complete response on RECIST 1.1 imaging at treatment end.

PET NPV rate: proportion of subjects in the analysis population who are considered to have NPV based on Hopkins Criteria scoring at treatment end.

Pathologic complete response (pCR) rate: proportion of subjects in the analysis population who have stable disease (SD) or partial response (PR) on RECIST 1.1 imaging at treatment end, who undergo salvage surgical resection and have a complete response determined on histologic evaluation.

Overall Complete Response (CR) rate: this is a composite proportion of subjects in the analysis population with a rCR, PET NPV, and pCR. This is the primary measure of efficacy for the study.

Overall Response Rate (ORR): proportion of subjects in the analysis population who have complete response (CR) or partial response (PR) based on RECIST 1.1 imaging at treatment end.

Progression-Free Survival (PFS): time from Day -7 treatment administration to the first documented disease progression or death.

Overall Survival (OS): time from Day -7 treatment administration to death due to any cause.

Locoregional Control (LRC): time from day -7 treatment to date of local or regional relapse within the primary radiation treatment field (relapse in the head or neck region, excluding CNS recurrence).

Rate of Distant Metastases (DM): proportion of subjects in the analysis population who develop distant recurrence, as defined by recurrence outside of the primary radiation treatment field (head and neck region).

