## 4.2.3.5 **Preliminary Results and Rationale for Expansion Cohort**

The current study has enrolled 27 patients from November 18, 2015 to August 6, 2016. The study is currently on hold for an interim safety and efficacy analysis. As of the data lock on September 14, 2016, 20 (74.1%) patients with HPV positive (p16 positive) disease and 7 (15.9%) with HPV negative (p16 negative) disease have enrolled. Early response data in imaged patients (n=9), shows a CR (CT and/or PET or pathologic CR on salvage surgery) in 8/8 (100%) of HPV positive patients and a PR in the single HPV negative patient. We anticipate easily hitting our primary endpoint of CR rate >60% in our HPV positive population based on these early results. However, based on our lack of HPV negative patients, it is unclear what responses will be seen.

Recent data analysis of an internal study (NCT01386632) using standard of care high-dose cisplatin (100 mg/m2 on days 1, 22, and 43) in a similar cohort of patients was performed. Distinct differences in response were seen in the HPV+ and HPV- groups, which mirror efficacy findings in similar studies. This analysis has revealed that 20 of 27 (74%) of evaluable patients with HPV positive disease achieved a CR (based on 3-month post-radiation CT and/or PET or subsequent salvage surgery). In the same study, the evaluable patients in the HPV negative cohort had 6 of 12 (50%) achieving the same CR endpoint.

Due to the historically good responses in HPV positive disease and the early findings in our current HPV positive cohort, we propose evaluation of efficacy separately in the HPV positive and HPV negative cohorts. As a result, we propose adding expansion cohorts after the interim analysis to explore efficacy in each of these unique populations. Addition of both HPV negative and HPV positive patients will provide further insight into efficacy of this novel combination.

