#### 7.1.2.6.3.3 PET Response (Hopkins Criteria)

Hopkins Criteria will be used to assess PET response when PET imaging is utilized. This is outlined in section 11.5. PET is not required, but is allowable to assist in determine the primary efficacy outcome when RECIST 1.1 data is considered not clinically representative of response. Patients without a RECIST 1.1 CR, but with a Hopkins Criteria negative predictive value (NPV) (See section 11.5) can forgo salvage surgery and be considered as having a CR in terms of the primary efficacy measure.

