#### 8.4.3 Statistical Methods

#### 8.4.3.1 Statistical Methods for Efficacy Analyses

The efficacy endpoints, analysis population, and statistical methods (including missing data handling) that will be employed for the efficacy analyses are presented in Table 7.

The primary endpoint is the total CR rate (composite outcome of rCR, PET NPV, and pCR) on all subjects. We have designed the study to test the hypothesis that the CR rate will be greater than 40.2% assuming a rate of 60.4%. To test this, we will use a one sample, one-sided asymptotic equality test with the null hypothesis that the total CR rate will be 40.2%. This test will result in a p-value greater than 0.05 if fewer than 21 patients respond to treatment. Secondary endpoints will include rCR, pCR, PET NPV, PFS, OS, LRC, and DM rates. For the secondary endpoints, we will only estimate confidence intervals to understand the possible range of values rather than doing formal hypothesis testing. Survival curves for PFS and OS will be constructed using the Kaplan-Meier method and 1 and 2-year survival estimates will be calculated.

Endpoint Statistical Method		Analysis Population	Missing data approach			
rCR Rate	Exact binomial method: Clopper-Pearson 95% confidence interval	FAS	Subjects with missing data are considered non-responders			
pCR Rate	Exact binomial method: Clopper-Pearson 95% confidence interval	FAS 	Subjects with missing data are considered non-responders			
CR Rate	One sample, one-sided asymptotic binomial test	FAS	Subjects with missing data are considered non-responders			
Objective Response Rate (CR + PR)	Exact binomial method: Clopper-Pearson 95% confidence interval	FAS	Subjects with missing data are considered non-responders			
PFS (RECIST 1.1) by independent radiology review	Summary statistics using Kaplan-Meier method	ASaT	Censored at last assessment date			
OS	Summary statistics using Kaplan-Meier method	ASaT	Censored at last assessment date			
LRC rate	Exact binomial method: Clopper-Pearson 95% confidence interval	FAS	Subjects with missing data are considered as disease not under control			
DM rate Exact binomial method: Clopper-Pearson 95% confidence interval		FAS	Subjects with missing data are considered as disease not under control			

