#### 8.4.7.1 Interim Efficacy Analysis

An interim analysis will also occur to evaluate efficacy. The interim analysis will occur after 27 patients are accrued to the study and have treatment end response assessments completed (imaging and if applicable, salvage surgical resection). This will occur at approximately 9 months after study initiation. In terms of efficacy, futility will be determined if 13 or fewer CRs (rCR +pCR) are seen in the 27 patients. If futility is not determined, the study will continue to accrue to final total of 34 HPV + patients and 23 HPV - patients who are evaluable for treatment response. This will be presented to and evaluated by the DSMB.

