## 8.4.7.3 Sample Size and Power Calculations

Sample size for this study will be powered based on the co-primary outcome of efficacy. Efficacy will be defined by the rCR rate at the treatment end imaging evaluation. The rCR rate will be defined by RECIST 1.1 criteria. Based on the Intergroup Trial evaluating the gold standard of high-dose bolus cisplatin 100 mg/m2 given on days 1, 22, and 43 of radiation at 70 cGy, the complete response rate was 40.2% [10]. This study included both HPV+ and HPV-patients with unresectable disease and did not differentiate response based on HPV status. Extrapolating on our data from the animal model, we anticipate at least a 50% improvement in this CR rate. Therefore, we estimated a CR rate of 60.4% with this study regimen in all-comers.

For the initial sample size calculation, Simon's two-stage design with the Minimax approach was utilized. The null hypothesis that the true response rate is 0.402 will be tested against a one-sided alternative. In the first stage, 27 patients were to be accrued. If there are 13 or fewer CRs in these 27 patients, the study will be stopped. Otherwise, 12 additional patients will be accrued for a total of 39. The null hypothesis will be rejected if 21 or more CRs are observed in 39 patients. This design yielded a type I error rate of 0.05 and power of 0.80 when the true CR rate is 0.604.

At the time of interim analysis, 27 patients are enrolled in the study. During this analysis, an internal analysis of a similar study (NCT01386632) using standard of care high-dose cisplatin

(100 mg/m2 on days 1, 22, and 43) in a similar cohort of patients was performed. Distinct differences in response were seen in the HPV+ and HPV- groups, which mirror efficacy findings in similar studies. This analysis has revealed that 20 of 27 (74%) of evaluable patients with HPV positive disease achieved a CR (based on 3-month post-radiation CT and/or PET or subsequent salvage surgery).

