Based on this new data, we have reassessed our power calculations for our HPV positive cohort, With this novel combination therapy we estimate that an improvement in efficacy of >20% to a CR rate of 90% would warrant future study of this regimen in HPV positive disease. Therefore, using a one-arm binomial design the null hypothesis that the true response rate is 74% will be tested against a one-sided alternative. The null hypothesis will be rejected if 31 or more CRs are observed in 34 patients. This design yields a type I error rate of 0.05 and power of 80% when the true response rate is 90%.

Reviewing the same data, the HPV negative cohort had 6 of 12 (50%) evaluable patients achieving a CR (based on 3-month post-radiation CT and/or PET or subsequent salvage surgery). Therefore, reassessing our power calculations for the HPV negative cohort in the proposed expansion cohort, we estimate a CR rate of 75% (50% improvement from the standard of care) with the study regimen would warrant future study of this regimen in HPV negative disease. Therefore, using a one-arm binomial sample size, the null hypothesis with a true response rate of 50% will be tested against a one-sided alternative. The null hypothesis will be rejected if 18 or more responses are observed in 23 patients. This design yields a type I error rate of 0.05 and power of 80% when the true response rate is 75%.

At the time of the interim analysis, 20 patients with HPV + disease are enrolled and 7 patients with HPV - disease are enrolled. Based on this reanalysis of sample size and power calculations, an additional 14 HPV positive patients and 16 HPV negative patients would need to be enrolled after the interim analysis.

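### The primary response is a composite that counts a negative PET, but the written futility rule omits PET and the opening of the sample size section names RECIST response alone

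*Combined protocol and SAP*

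**What the plan says.** The statistical plan is section 8 of the protocol. It describes complete response in three ways.

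- **Composite, PET included.** Section 8.4.1: "Overall Complete Response (CR) rate: this is a composite proportion of subjects in the analysis population with a rCR, PET NPV, and pCR". It names this the primary measure. Section 8.4.3.1 repeats it: "The primary endpoint is the total CR rate (composite outcome of rCR, PET NPV, and pCR) on all subjects". Section 7.1.2.6.3.3 says that a patient without a RECIST CR but with a negative Hopkins score "can forgo salvage surgery and be considered as having a CR in terms of the primary efficacy measure". Section 7.1.2.6.3.4 lists the same three components.
- **Radiographic plus pathologic, PET omitted.** Section 8.4.7.1: "futility will be determined if 13 or fewer CRs (rCR +pCR) are seen in the 27 patients".
- **RECIST alone.** The opening of 8.4.7.3: "Efficacy will be defined by the rCR rate at the treatment end imaging evaluation".

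Two other places show how responses were scored in practice. The benchmark rates for the HPV cohorts come from an internal study, with patients "achieving a CR (based on 3-month post-radiation CT and/or PET or subsequent salvage surgery". The trial's own early tally in 4.2.3.5 "shows a CR (CT and/or PET or pathologic CR on salvage surgery) in 8/8 (100%) of HPV positive patients".

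On pathology, 8.4.1 restricts pCR to patients with stable disease or partial response on imaging. Section 7.1.2.6.3.2 also sends patients with imaging progression to surgery to establish pathologic response, and 7.1.2.6.3.4 brings into the analysis a pathologic CR in a patient who lacks a RECIST CR, with no exception for imaging progression.

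**The concern.** A stopping rule should count the same event as the test it protects. Here one identifiable type of patient falls between the two: no RECIST CR, negative PET, no surgery. In the final test that patient is a CR. Under 8.4.7.1 the patient is neither rCR nor pCR and, having forgone surgery, cannot become a pCR. The rule as written therefore sets a harder hurdle at 27 patients than the design calculation assumed.

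At stake are whether the trial could stop for futility on a count that its own primary definition would not support, and which count was used if the look has already taken place. For pCR after imaging progression, two analysts following different sections would score the same patient differently.

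**Working it through.** **Side-by-side reading.** Section 8.4.1 defines rCR as RECIST 1.1 imaging and lists the PET result as a separate component, and 8.4.7.3 ties rCR to RECIST 1.1 again. So rCR + pCR cannot be read as shorthand that includes PET.

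| Patient at treatment end | 8.4.1 and 8.4.3.1 | 8.4.7.1 | 8.4.7.3 (opening) |
|---|---|---|---|
| RECIST CR | CR | CR | CR |
| No RECIST CR, PET negative, no surgery | CR | not CR | not CR |
| SD or PR on imaging, pathologic CR | CR | CR | not CR |
| PD on imaging, pathologic CR | not pCR under 8.4.1; counted under 7.1.2.6.3.4 | unclear | not CR |

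Only the composite matches the way the 74% and 50% benchmarks and the early tally were scored.

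**Inputs.** Stop at 13 or fewer of 27; reject at 21 or more of 39; null 0.402, alternative 0.604 (8.4.7.3). Cohort null rates 0.74 and 0.50, targets 0.90 and 0.75 (8.4.7.3). Enrolled mix: "At the time of the interim analysis, 20 patients with HPV + disease are enrolled and 7 patients with HPV - disease are enrolled". The share of patients who are CR by PET alone, q, is not in the documents; I assume 3, 5 and 8 points, which is 27q = 0.8, 1.4 and 2.2 patients of 27.

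**Reproducing the plan's figures.** With X1 ~ Bin(27, p) and X2 ~ Bin(12, p), P(reject) is the sum over x = 14 to 27 of P(X1 = x) × P(X2 ≥ 21 − x). At p = 0.402 this is 0.0498, and at p = 0.604 it is 0.801, matching the stated 0.05 and 0.80. The stop chance at 0.604 is P(X1 ≤ 13) = 0.135.

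**Original all-comer design, PET omitted at the interim only.** The stage 1 count is Bin(27, 0.604 − q). Each patient not counted then is a PET-only CR with probability q / (1 − 0.604 + q) and returns to the final composite count. Stage 2 is Bin(12, 0.604).

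| q | Stop chance, true composite rate 0.604 | Power |
|---|---|---|
| 0 | 13.5% | 0.80 |
| 3 points | 21.8% | 0.74 |
| 5 points | 28.5% | 0.68 |
| 8 points | 40.1% | 0.58 |

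**Current cohort hypotheses.** The interim count is Bin(20, p+ − q) + Bin(7, p− − q), and the stop chance is P(total ≤ 13).

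| q | Targets 0.90 / 0.75 | Benchmarks 0.74 / 0.50 |
|---|---|---|
| 0 | 0.0002% | 2.4% |
| 3 points | 0.002% | 5.2% |
| 5 points | 0.009% | 8.1% |
| 8 points | about 0.05% | 14.4% |

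**The case against.** The strongest reply is that the primary definition is not in doubt. Section 8.4.1 says outright which measure is primary, and three other sections agree. The RECIST sentence introduces the original sample size calculation and looks like leftover text; the cohort paragraphs later in 8.4.7.3 rest on CT, PET or surgery. The early tally counted PET, so the trial may never have applied the narrower count. This stands as an argument that the repair is easy. It does not remove the conflict, because 8.4.7.1 is the current stopping rule and no other text overrides it.

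The reply is also right about size. The benchmark rates are the current null rates, so stopping more often there is not a wrongful stop. The enrolled mix has a null rate of (20 × 0.74 + 7 × 0.50) / 27 = 67.8%, so 60.4% lies below it. The 13.5% to 40.1% range is a loss only under the original 40.2% versus 60.4% design, which 8.4.3.1 and 8.4.7.3 still print.

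A reader might also infer that pathology can only add responders and so inflates false success, because no rule removes an imaging CR when surgery finds cancer. The documents do not support that as a finding. It is an inference from silence. The benchmark CR is described in nearly the same terms as the trial's, so the same upgrade may sit in both, and surgery before treatment end imaging is scored as progression, which runs the other way. Section 4.2.3.1 also plans a second analysis of pathologic and radiographic response.

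**Conclusion.** The inconsistency is real: the final test counts a PET-only CR, and the written futility rule and the opening of 8.4.7.3 do not. The conflict over pCR after imaging progression is also real, but its frequency is unknown.

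The effect on error rates depends on which design is meant. For the original all-comer design at 60.4%, an assumed PET-only share of 3 to 8 points raises the stop chance from 13.5% to between 21.8% and 40.1% and lowers power from 0.80 to between 0.74 and 0.58. For the current cohort targets the stop chance is about 0.05% at most. It would be wrong to conclude that the present cohorts face a material risk of being stopped in error. Section 4.2.3.5 describes a 2016 hold for the interim and the protocol version is dated 2018, so the look may already have been run. What then matters is which count was applied and reported.

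A minor gap remains: the text does not say how residual cancer found at treatment end surgery is scored after an imaging CR. No direction or size of bias can be claimed from that.

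**What to change.** 1. In 8.4.7.1, replace the rCR + pCR count with the composite CR of 8.4.1. In the opening of 8.4.7.3, replace the RECIST rCR rate with the same composite.
2. If the interim has been run, report its count both ways (rCR + pCR, and composite) and state which was applied to the rule.
3. Reconcile 8.4.1 with 7.1.2.6.3.2 and 7.1.2.6.3.4 on whether a pathologic CR after imaging progression counts toward the primary measure.
4. Keep the primary count as defined, and add a sensitivity count in which patients with an imaging CR and residual cancer at treatment end surgery are non-CR.

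The cost is amendment wording and one extra tabulation from data already collected. Because early responses have been seen, the amendment should be dated and should give its reason, namely agreement with the existing primary definition and with the benchmarks.

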#### 3.2 Secondary Objective(s) & Hypothesis (es)

1. **Objective:** To estimate progression-free survival (PFS), overall survival (OS), the locoregional control rate (LRC), and distant metastases (DM) rate at 1- and 2-years in subjects treated with pembrolizumab given in combination with CRT.

**Hypothesis**: The addition of pembrolizumab to standard CRT will show increased efficacy in terms of key survival endpoints utilized in head and neck cancer.

2. **Objective:** To determine the best overall response rate (ORR) as defined by RECIST 1.1 at treatment end imaging in subjects with Stage III-IVB SCCHN treated with pembrolizumab given in combination with CRT.

**Hypothesis**: The addition of pembrolizumab to standard CRT will show superior ORR compared to historical controls.

4. **Objective:** To estimate the quality of life (QOL) of subjects with Stage III-IVB SCCHN treated with pembrolizumab in combination with CRT during therapy, treatment end, and 1- and 2-years following treatment.

**Hypothesis**: Acute and long-term QOL of participants treated with the combination of pembrolizumab and low dose weekly cisplatin and radiation will be superior to historical controls.

5. **Objective:** To correlate ORR, PFS, OS, LRC, and DM with tumor PD-L1 expression in subjects with Stage III-IVB SCCHN treated with pembrolizumab in combination with CRT.

**Hypothesis**: High PD-L1 expression has correlated with responses in the metastatic setting and will correlate with key disease response and survival outcomes in the curative intent setting.

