13. Patients with residual disease (SD, PR, or PD) on post-treatment imaging will undergo salvage surgical resection (at the discretion of the surgeon) if their disease is felt curable with salvage surgery. Additionally, patients with a CR and clinical suspicion for viable residual disease will be offered salvage surgery. Following pathology analysis, salvage surgical tissue will be sent for correlative studies. Detailed instructions for tissue collection, processing, and shipment are included in the procedures manual.

14. PET imaging at baseline and treatment end is not required for the study, but is allowed for use to determine complete response rate when tumor response on standard imaging cannot confirm CR based on RECIST 1.1. Please see sections 7.1.2.6.2 and 7.1.2.6.3 for details.

15. Screening labs completed within 7 days (168 hours) of treatment initiation (day -7) will not need to be repeated.

16. Once a subject experiences confirmed disease progression or starts a new anti-cancer therapy, the subject moves into the Survival Follow-Up Phase. These subjects will be followed every 6 months to assess for survival status until death, withdrawal of consent, or the end of the study, whichever occurs first.

17. If a subject discontinues pembrolizumab, return visit timing is left to treating physician discretion until day 150 although it is highly recommended that the subject return for Day 78, 120, and 150 so research specimens and QOL can be collected.

18. Minimum interval between pembrolizumab doses is 14 days.

19. Vital signs and weight do not need to occur on the same day as the visit but need to be completed within the window and prior to the next treatment.

20. Once a subject transitions to follow-up all documented AEs will be followed until resolution or to a new baseline as determined by the treating investigator. Only new AEs that could be considered an ECI or irAR will be documented and followed while in follow-up.

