#### 7.1.2.6.3.4 Salvage Surgery

Patients with residual disease considered resectable after all their planned therapy is completed may undergo a salvage surgical procedure, if that procedure is conceived as potentially curative.

PET imaging can be used to guide post treatment surgical need. The preference of the study would be to recommend no further therapy for any PET tumor avidity (CMR). However, this is not a requirement and will be left up to the discretion of the treating surgical oncologist.

Patients achieving a complete response who had advanced (N2 or greater) neck disease at presentation should be considered for an elective neck dissection after completion of all of their planned therapy if the post therapy imaging or clinical exam indicates persistent disease, despite RECIST 1.1 response. The nature of the neck dissection will be at the discretion of the treating head and neck surgeon.

Pathologic response to therapy will be evaluated following surgery. Pathological complete response (pCR) is defined as the absence of residual invasive and in situ cancer on hematoxylin and eosin evaluation of the completely resected sites of residual disease. Subjects who have a pathologic CR, but do not have a RECIST 1.1 CR will be included in the final efficacy analysis. This analysis will include the composite outcome of patients with RECIST 1.1 CR, Hopkins Criteria NPV (see section 11.5), and pathologic CR.

Patients who show signs of clear, clinical progression prior to the treatment end imaging may be considered for surgery. This will be at the discretion of the treating providers, including the surgeon, medical oncologist, and radiation oncologist. Patients who undergo surgery will be determined to have PD in terms of analysis of the primary endpoint.

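### Locoregional control is defined by relapse alone, so read literally a tumour that never cleared, or was resected with viable cancer, is not an LRC failure

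*Combined protocol and SAP*

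**What the plan says.** Section 8.4.1 defines LRC as "time from day -7 treatment to date of local or regional relapse within the primary radiation treatment field". The parenthesis that follows again speaks of relapse, in the head or neck region and excluding the CNS. In the same list, the PFS event is documented disease progression or death. The objective in Section 3.2 is to estimate "the locoregional control rate (LRC), and distant metastases (DM) rate at 1- and 2-years".

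Table 7 (Sections 8.4.3.1 and 8.4.3.2) analyses LRC in the FAS as a binomial proportion with a Clopper-Pearson 95% interval. Its missing-data rule is: "Subjects with missing data are considered as disease not under control".

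The plan expects residual disease after chemoradiotherapy. Flow-chart footnote 13 (after Section 6.3) says: "Patients with residual disease (SD, PR, or PD) on post-treatment imaging will undergo salvage surgical resection", subject to the surgeon's discretion and to the disease being felt curable. Section 7.1.2.6.3.4 says: "Patients with residual disease considered resectable after all their planned therapy is completed may undergo a salvage surgical procedure". For surgery before the treatment-end scan, that section adds: "Patients who undergo surgery will be determined to have PD in terms of analysis of the primary endpoint". Section 8.4.2.2 also scores such patients as PD in the efficacy analysis.

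Section 4.2.3.1 says that LRC and the other secondary endpoints will be compared with historical data and may be considered when deciding whether to go forward. The related hypothesis in Section 3.2 is: "The addition of pembrolizumab to standard CRT will show increased efficacy in terms of key survival endpoints utilized in head and neck cancer".

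**The concern.** After definitive chemoradiotherapy, locoregional failure can take two forms: the tumour clears and returns, or it never clears. The LRC definition names only the first. A tumour that never cleared cannot relapse in the ordinary sense of the word, and the plan gives no LRC event or event date for that patient.

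Take a patient with PR at about day 150 who has salvage surgery, viable cancer in the specimen and no later recurrence. For the primary endpoint this is a non-CR. For LRC, read literally, the patient is controlled from Day -7 onward, and the surgeon's result is credited to pembrolizumab plus CRT. A patient with stable residual disease and no surgery is scored the same way.

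At stake is the meaning of a secondary endpoint that Section 4.2.3.1 names as possible input to the go-forward decision. Sections 3.2 and 8.4.7.4 also use LRC for the PD-L1 and HPV comparisons, where scoring persistence as control could blur a real difference.

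**Working it through.** The plan states no LRC rate, event count or power, so there is no LRC figure to reproduce. The check has two parts.

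**1. Does any other rule catch this patient?**

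- *Table 7 missing-data rule.* It applies when data are missing. Residual tumour on a scan or in a specimen is observed data.
- *Surgery scored as PD (Sections 7.1.2.6.3.4 and 8.4.2.2).* This covers only surgery before the treatment-end scan, and Section 7.1.2.6.3.4 ties it to the primary endpoint. PD is also not the LRC event.
- *Time or proportion.* Section 8.4.1 defines LRC as a time and Table 7 analyses a proportion. With no event the patient is censored in the first and a success in the second.
- *Move to survival-only follow-up (Sections 7.1.1.5.3 and 7.1.5.6).* This needs confirmed progression or new anti-cancer therapy. The plan does not say whether salvage surgery counts as such therapy. If it does, later LRC status may be missing and be scored as not controlled, a partial offset. Stable residual disease on scheduled imaging is not affected.

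No rule closes the gap.

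**2. How many patients could be affected?**

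Inputs: 34 HPV+ and 23 HPV- patients (Section 5.1.1); target CR rates of 90% and 75% (Section 3.1); null CR rates of 74% and 50% (Section 8.4.7.3). All 57 are assumed to be in the FAS.

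Expected non-CRs = 34 × (1 − CR in HPV+) + 23 × (1 − CR in HPV-).

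- Target rates: 34 × 0.10 + 23 × 0.25 = 3.40 + 5.75 = 9.15; 9.15/57 = 16.1%.
- Null rates: 34 × 0.26 + 23 × 0.50 = 8.84 + 11.50 = 20.34; 20.34/57 = 35.7%.

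These are ceilings. Some non-CRs will later have a recorded locoregional relapse and be counted anyway.

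Effect per affected patient: 1/57 = 1.75 points overall, or 1/23 = 4.3 points within the HPV- cohort.

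Illustration, assuming 6 recorded relapses (an assumption, not a figure from the plan):

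| Persistent cases counted as failures | LRC rate | 95% CI |
|---|---|---|
| 0 (as written) | 51/57 = 89.5% | 78.5 to 96.0 |
| 3 | 48/57 = 84.2% | 72.1 to 92.5 |
| 6 | 45/57 = 78.9% | 66.1 to 88.6 |
| 9 | 42/57 = 73.7% | 60.3 to 84.5 |

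With 4 or 8 relapses instead, the as-written rate is 53/57 = 93.0% or 49/57 = 86.0%. The drop per persistent case stays at 1.75 points.

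**The case against.** The strongest reply is that the text is silent rather than wrong. Section 3.2 speaks of a control rate, Table 7 uses the language of disease not under control, and an analyst could score viable residual tumour as uncontrolled on that basis. The bias would then be zero. This stands as a limit on size. It does not cure the definition: the Table 7 wording governs missing data only, and the result would rest on an unwritten interpretation.

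A second reply is that salvage surgery is called standard of care in Section 2.1, so control including salvage is a coherent quantity. That is fair, but the plan does not say that this is what LRC measures.

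A third is that counting all residual disease as failure could bias LRC the other way. PET is optional and surgery is discretionary, so a CT-only PR may never be verified as viable tumour. Section 7.1.2.6.3.3 itself allows that RECIST may misrepresent response. This stands, and the fix needs a sensitivity analysis for it.

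LRC is also secondary, unpowered and reported by confidence interval only, so no test, sample size or stopping rule changes.

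A reader might infer that the historical comparison is biased in favour of the regimen. The documents do not support that, because they do not give the LRC definition used in the historical studies. If those also count relapse only, the comparison may be fair.

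**Conclusion.** The concern holds as a gap in the definition. On the literal text of Section 8.4.1, observed persistence of locoregional disease is not an LRC failure. Within the trial, leaving it out can only raise the LRC rate, by 1.75 points for each such patient without a later recorded relapse. Scoring later status as missing, if salvage surgery counts as new anti-cancer therapy, would offset part of this.

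A reader might take 16% or 36% as the size of the overstatement, or halve them to about 8 and 18 points. The documents support neither. The first pair are ceilings that assume every non-CR has no later locoregional event, and nothing in the plan justifies one half or any other fraction. The true size may be zero. The ceiling is higher in the HPV- cohort (25% to 50% non-CR, against 10% to 26% in HPV+), but an actual difference in bias would also depend on how often residual disease is salvaged or stays stable in each cohort.

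The change is worth making because LRC may inform the go-forward decision and the correction is small.

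**What to change.** In Section 8.4.1, define LRC failure as the earliest of:

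- (a) persistent locoregional disease at treatment end that is not a composite CR, including viable tumour in a salvage specimen, dated at the treatment-end scan;
- (b) locoregional progression leading to surgery before that scan;
- (c) later local or regional relapse or progression.

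Add a sensitivity analysis in which residual disease seen on CT only, without PET or pathology, is not a failure unless it later progresses. Report LRC including successful salvage as a separate descriptive figure. Say whether salvage surgery counts as new anti-cancer therapy when LRC status is derived. Match the definition to the historical comparator where possible.

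The cost is one definition and a little more analysis. The treatment-end imaging and surgical pathology are already planned, although viability will not be established in every patient. The LRC figure may be less favourable, and it will track the primary endpoint more closely. No treatment, procedure, test or sample size changes.
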